4.2.4.2 Extended Safety endpoints

Extended Safety endpoints include:

- Type, frequency and severity of adverse events and relationship to luspatercept (per NCI CTCAE version 4.0) up to final database lock

4.3 Stratification, Randomization, and Blinding

Subjects were randomized to receive luspatercept or placebo at a 2:1 ratio. Randomization was accomplished by an IVRS/IWRS to ensure timely registration and randomization. A stratified randomization schedule was implemented. Randomization was stratified by the following geographical regions:

- North America and Europe (including Bulgaria, Canada, France, Greece, Italy, United Kingdom and United States)
- Middle East and North Africa (including Israel, Lebanon, Tunisia and Turkey)
- Asia-Pacific (including Australia, Malaysia, Taiwan and Thailand)

4.4 Sample Size Determination

Based on data in the luspatercept Phase 2 (A536-04/A536-06) studies, the assumed targeted response rate for the primary endpoint is 40% in the luspatercept group and 20% for the placebo group. A total sample size of 300 subjects (200 in the luspatercept group, 100 in the placebo group) will have 90% power to detect the difference between the luspatercept group and the placebo group with a 2-sided alpha of 0.05 and assumed 10% drop-out rate for each treatment group.

5. GENERAL STATISTICAL CONSIDERATIONS

5.1 Reporting Conventions

Summary tables, listings, figures and any supportive SAS outputs will include a “footer” of explanatory notes that will indicate, at a minimum, the following:

- Program source (e.g., SAS program name, including the path, that generates the output) and
- Data extraction date (e.g., the data cutoff date, database lock date, run date).

The purpose of the data extraction date is to link the output to a final database, either active or archived, that is write-protected for replication and future reference. An output date will also appear on each output page and will indicate the date the output was generated by the analysis program.

The following reporting conventions apply generally to tables, listings, and figures:

- Data from all study centers will be combined for analysis;
- All stratified efficacy analyses will use randomization factor as stratum;
- All statistical tests of the treatment effect will preserve a significance level of 0.050 for 2-sided tests. Testing of interactions will be performed at the 0.100 significance level, unless specified otherwise;
- P-values will be rounded to 4 decimal places. P-values that round to 0.0000 will be presented as ‘<0.0001’ and p-values that round to 1.000 will be presented as ‘>0.9999’;
- Confidence intervals (CIs) will be presented as 2-sided 95% CIs unless specified differently in specific analysis;
- Summary statistics will consist of the number and percentage of subjects (or cycles, if appropriate) in each category for discrete variables, and the sample size, mean, median, Standard Deviation (SD), Q1, Q3, minimum, and maximum for continuous variables;
- All mean, median, Q1, and Q3 values will be formatted to one more decimal place than the measured value. Standard deviation values will be formatted to two more decimal places than the measured value; Minimum and maximum values will be presented to the same number of decimal places as the measured value.
- All percentages will be rounded to one decimal place. The number and percentage of responses will be presented in the form XX (XX.X%), where the percentage is in the parentheses; when

the number of a response is zero, percentage will not be presented for that response;

- All listings will be sorted for presentation in order of treatment group, study center, subject, and date of procedure or event if not otherwise specified.
- All listings will display original collected values, cases with special marks (i.e., <500) will be listed as it is. The special mark will be removed if the value is used for calculation in tables.
- All analysis and summary tables will have the analysis population sample size (i.e., number of subjects) if not otherwise specified;
- All summary tables will be displayed by treatment (“Luspatercept + BSC” and “Placebo + BSC”), the “Total” group will be added for sections if specified;
- The day of the first dose of IP will be defined as Day 1; for erythroid response related endpoint, if a subject is not treated, the randomization date will be used as Day 1.
- In general, if not otherwise specified, baseline value will be defined as the last value (including “unscheduled”) on or before the date of the first dose of IP (if collecting time is available, date/time will be used to compare with first dosing date/time to identify baseline record, if there is no time available, only date will be used); if multiple values are present for the same date/time, the average of these values will be used as the baseline. For subjects who were not treated, the value on or prior to randomization date will be used. Specifically, for the laboratory hematology parameter ‘Leukocytes’, the baseline is defined as the highest value between screening visit and dose 1 day 1 visit.
- For data handling in change from baseline and shift tables (except for MRI and DXA parameters), “unscheduled” visits will be grouped with the closest scheduled visit based on assessment date. The average will be used as value for that scheduled visit in change from baseline tables; the worst category will be used in shift tables. If an unscheduled visit has equal distance to two scheduled visits, it will be grouped with the later visit. Specifically, for ADA titer summary, the titer value won’t be averaged if an “unscheduled” visit is mapped to the closest scheduled visit. The titer for “unscheduled” visit will only be used for summary if the original scheduled visit has no titer result.
- For RBC transfusion related efficacy endpoints summary, the 12-week interval before Week 48 is defined as:

Baseline 12-week interval: from Day -83 to Day 1;
Week 1 - 12 interval: from Day 2 to Day 85;
Week 13 - 24 interval: from Day 86 to Day 169;
Week 25 - 37 interval: from Day 170 to Day 253;
Week 37 - 48 interval: from Day 254 to Day 337.
- For RBC transfusion related efficacy endpoints summary beyond the 48-week double-blinded

treatment period, the 12-week interval is defined as:

Week 49 - 60 interval: from Day 338 to Day 421;
Week 61 - 72 interval: from Day 422 to Day 505;
Week 73 - 84 interval: from Day 506 to Day 589;
Week 85 - 96 interval: from Day 590 to Day 673;
Week 97 - 108 interval: from Day 674 to Day 757;
Week 109 - 120 interval: from Day 758 to Day 841;
Week 121 - 132 interval: from Day 842 to Day 925;
Week 133 - 144 interval: from Day 926 to Day 1009;
Week 145 - 156 interval: from Day 1010 to Day 1093;
Week 157 - 168 interval: from Day 1094 to Day 1177;
Week 169 - 180 interval: from Day 1178 to Day 1261;
Week 181 - 192 interval: from Day 1262 to Day 1345;
Week 193 - 204 interval: from Day 1346 to Day 1429;
Week 205 - 216 interval: from Day 1430 to Day 1513;
Week 217 - 228 interval: from Day 1514 to Day 1597.

All the data collected up to 11MAY2018 were used for summary in the primary CSR. The final database will be locked when everyone rolls over to a long-term follow-up study. All data collected up to the time of every subject rolling over to the long term follow up study will be used for summary. Data selection rules will be applied in each summary panel as needed, please refer to relevant sections for details.

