### 7.2. Treatment Administration and Schedule

Luspatercept or placebo will be administered as a subcutaneous (SC) injection to subjects by the study staff at the clinical site and administration will be documented in the subject's source record. Subcutaneous injections will be given in the upper arm, thigh, and/or abdomen. Calculated doses requiring reconstituted volume greater than 1.2 mL should be divided into separate similar volume injections across two separate sites using the same anatomical location but on opposite sides of the body (example left thigh and right thigh). The maximum volume per SC injection should not exceed 1.2 mL. The maximum total dose per administration should not exceed 120 mg, which results in 2.4 mL maximum total volume after reconstitution. The injection sites can be rotated according to Investigator judgment, and the injections can be given in the following order as needed, for example: 1) right upper arm, 2) left upper arm, 3) right upper thigh, 4) left upper thigh.

Subjects will be assigned to treatment as per one of the following regimens:

- Luspatercept starting dose level 1 mg/kg SC once every 21 days
- Placebo SC once every 21 days

The investigational product should be administered according to the following criteria:

- **Pre-treatment/ pre-transfusion** Hb value is  $< 11.5$  g/dL and increase of Hb  $\leq 2.0$  g/dL compared to the pre-dose Hb of Day 1 of the previous treatment dose cycle, and
- Any related adverse events must be  $< \text{Grade } 2$  according to NCI CTCAE criteria ([Appendix C](#))
- WBC  $< 3 \times$  baseline. Corrected WBC values should be used to establish the baseline WBC. Baseline is equal to the highest WBC value between Screening WBC and Study Dose 1 Day 1.
- Leukopenia, neutropenia and/or thrombocytopenia should be  $< \text{Grade } 3$ , as per NCI CTCAE criteria ([Appendix C](#))
- $< 50 \%$  increase from baseline in transfusion burden in combination with shift from baseline (worsening) of  $< 2$  grades in leukopenia, neutropenia or thrombocytopenia

Please refer to [Table 5](#) for guidelines on dose modifications and dose delays.

Subjects must have Hb assessed and results available prior to each study drug administration. If a transfusion occurred prior to dosing, the pre-transfusion Hb should be considered for dosing purposes (ie, Hb  $\geq 14$  days post- transfusion).

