11.4.1 Hematology/Chemistry/Immunology

The laboratory results and change from baseline will be summarized by visit by treatment group for central lab hematology and chemistry panels separately.

A shift table representing the shift from the baseline grade to maximum NCI-CTC Grades (high or low) will be provided for selected hematology and chemistry parameters having toxicity grade by visit by treatment group. The shift summary for high category will be done for hepatic function parameter (ALT, AST, ALP, and total bilirubin) and renal function parameter (serum creatinine). The shift summary for low category will be done for hematology parameter (platelets, leukocytes and absolute neutrophil counts).

To estimate the incidence of subjects who have passed the predefined threshold for selected parameters, a summary table representing the number and percentage of subjects with lab assessments satisfying the threshold criteria will be provided by treatment group. A subject with post-baseline result (including “unscheduled” visits) meeting the criteria will be counted. The threshold criteria includes below:

LIVER FUNCTION	
Post-baseline Alanine Aminotransferase (ALT)	$\geq 3x$ upper limit of normal (ULN)
Post-baseline Aspartate Aminotransferase (AST)	$\geq 3x$ ULN
Post-baseline Direct Bilirubin (BILDIR)	$\geq 2x$ ULN

Post-baseline Total Bilirubin (BILTOTAL)	$\geq 2x$ ULN
Post-baseline ALT/AST and BILDIR	(ALT $\geq 3x$ ULN or AST $\geq 3x$ ULN) and BILDIR $\geq 2x$ ULN
Post-baseline ALT/AST and BIL TOTAL	(ALT $\geq 3x$ ULN or AST $\geq 3x$ ULN) and BIL TOTAL $\geq 2x$ ULN

RENAL FUNCTION	
Post-baseline Creatinine Clearance (CREATCLR)	< 0.5x baseline
Post-baseline Serum Creatinine (CREAT)	> 2x baseline
Albuminuria Category (ACR: mg/g)	<30
	≥30- ≤300
	>300-≤1000
	>1000-≤3500
	>3500
HEMATOLOGY	
Post-baseline Leukocytes (WBC)	≥ 2x baseline and > ULN
	≥ 3x baseline and > ULN
	≥ 2x baseline and > ULN and lasts for at least 42 days
	≥ 3x baseline and > ULN and lasts for at least 42 days
Maximum Post-baseline Platelets (PLAT)	≥ 1.5x baseline and > ULN
	≥600 - <1000x10 ⁹ /L

	$\geq 1000 \times 10^9/L$
--	---------------------------

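### The highest-of-two leukocyte baseline, written for WBC-multiple dosing criteria, builds a downward shift into within-arm leukocyte change and leukopenia shift tables

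*SAP*

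**What the plan says.** SAP 5.1 opens its list with "The following reporting conventions apply generally to tables, listings, and figures". Within that list it sets a default: "In general, if not otherwise specified, baseline value will be defined as the last value" on or before the first dose of IP. It then makes an exception for the hematology parameter Leukocytes: "the baseline is defined as the highest value between screening visit and dose 1 day 1 visit".

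SAP 11.4.1 gives no other leukocyte baseline. Three outputs there use one:

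- Change from baseline: "The laboratory results and change from baseline will be summarized by visit by treatment group for central lab hematology and chemistry panels separately".
- The shift table from baseline grade to maximum grade, in the low direction: "The shift summary for low category will be done for hematology parameter (platelets, leukocytes and absolute neutrophil counts").
- The threshold rows for leukocytes, such as "≥ 2x baseline and > ULN", with a matching >=3x row and versions lasting at least 42 days.

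The exception comes from the protocol. Section 7.2, in the criterion that WBC be below 3 times baseline, states: "Baseline is equal to the highest WBC value between Screening WBC and Study Dose 1 Day 1". Table 5, footnote e, repeats the definition and is attached to the two WBC-count rows (>=2x and >=3x baseline). The SAP gives no reason for carrying the rule into the descriptive tables.

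**The concern.** The larger of two readings is, on average, higher than a subject's usual level whenever there is any within-subject variation. A single later reading carries no such upward selection. Subtracting the first from the second therefore gives a negative expected change when nothing has happened. In the shift table, the baseline leukopenia grade is set from the better of two readings, so later readings have more room to look worse than to look better.

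The shift table is also inconsistent within itself. Its platelet and neutrophil rows fall under the default (last pre-dose value) while its leukocyte row does not. Neutrophils are part of the leukocyte count, yet the two rows start from different baseline rules.

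What is at stake is the reading of within-arm leukocyte summaries. Cytopenias and WBC rises trigger actions in protocol Table 5, and SAP 11 reports luspatercept columns that extend into the open-label phase, where there is no concurrent placebo group. A reader could take an apparent fall in WBC, or a tilt towards leukopenia, for a drug effect when the baseline rule alone produced it.

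**Working it through.** The documents give no figure for this effect, so there is none to reproduce. They also give no within-subject variability for WBC; all CVs below are assumptions.

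**Inputs from the documents.** The leukocyte and default baselines are in SAP 5.1. Two pre-dose samples are expected: protocol Table 3 schedules hematology within 4 weeks before Dose 1 Day 1 and again on that day, and Section 6.2 requires the Day 1 hematology even if screening was within 72 hours.

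**Mean change with no true effect.** For two independent normal readings with mean mu and within-subject SD sigma, E[max] = mu + sigma/sqrt(pi) = mu + 0.564 sigma. The expected change is therefore -0.564 sigma, against 0 with the last value. For lognormal readings, E[max] = mean x 2 x Phi(s/sqrt 2), with s = sqrt(ln(1 + CV^2)):

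| Assumed CV | Normal, -0.564 x CV | Lognormal, exact | Lognormal, simulated | Last value |
|---|---|---|---|---|
| 15% | -8.5% | -8.4% | -8.4% | 0 |
| 20% | -11.3% | -11.1% | -11.2% | 0 |
| 30% | -16.9% | -16.4% | -16.5% | 0 |

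At CV 20%, a true 10% rise would be reported as a mean change of about -1.2%.

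**Share of subjects showing a fall.** With three exchangeable readings (two pre-dose, one later), the later one is the highest with probability 1/3. So 2/3 of subjects show a fall at a given visit, whatever the CV, against 1/2 with the last value.

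**If the two pre-dose readings are correlated.** With correlation rho, the shift is -sigma x sqrt((1 - rho)/pi). At rho = 0.5 and CV 20% this is 20% x 0.399 = 8.0%. If the later reading is independent of both, the chance that it exceeds both is 1/4 + arcsin((1 + rho)/2)/(2 pi) = 0.25 + 0.848/6.283 = 0.385, so about 62% show a fall.

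**Leukopenia shifts.** This was simulated with no true change. Assumptions: CV 20%, LLN 4.0 x10^9/L, median WBC 5.0 or 7.0 (between-subject log SD 0.35 or 0.40), 16 independent visits. Grade limits below LLN were 3.0, 2.0 and 1.0, matching those quoted in the footnotes to protocol Table 5.

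| Assumed median WBC | Baseline | One visit: worse / better | Worst of 16 visits: worse |
|---|---|---|---|
| 5.0 | last value | 13.7% / 13.6% | 51.5% |
| 5.0 | highest of two | 18.6% / 5.7% | 59.4% |
| 7.0 | last value | 5.7% / 5.7% | 25.8% |
| 7.0 | highest of two | 7.5% / 2.1% | 29.2% |

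The one-visit shifts are balanced under the last value and tilted towards worsening under the highest value. Worst-over-visits counts are one-sided under either rule; the highest-value baseline adds about 3 to 8 percentage points.

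**Between-arm difference.** Both readings precede dosing, so the offset is the same on average in both randomized arms. At CV 20% the simulated changes for true multipliers of 1.0 and 1.1 are 0.0% and 10.0% with the last value, and -11.2% and -1.2% with the highest. The difference is 10 points either way.

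**The case against.** The strongest defence is that the rule is disclosed, prespecified and taken from the protocol. Protocol 7.2 states the highest-value baseline and, two criteria later, uses a shift from baseline in leukopenia as a dosing criterion without giving another leukocyte baseline. One baseline throughout is therefore a possible reading. Against that, footnote e of Table 5 is attached to the WBC-count rows and not to the leukopenia-shift row. Nothing in the dosing text supplies a reason to use a maximum of two readings for mean change. The point that two leukocyte baselines would then appear in adjacent tables is fair and is the cost of the fix.

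Several stronger readings are tempting but unsupported:

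- **That leukocytosis is hidden.** The threshold rows count a subject with any qualifying post-baseline result, including unscheduled visits. For a sustained 2.2-fold rise at CV 20% over 16 independent visits, about 98% (last value) and 96% (highest value) reach 2 times baseline at least once, ignoring the ULN condition. The gap is wider for a 1.5-fold rise (about 61% against 40%), but reaching 2 times baseline there mostly reflects noise. These rows mirror the dosing criteria, so keeping the protocol's baseline in them is defensible. Observed values by visit, WBC plots over time, CTCAE grades, adverse event tables and listings do not depend on the baseline.
- **That the luspatercept-placebo comparison is biased.** For the randomized difference in mean change it is not, as shown above.
- **That leukocytes are the only laboratory exception.** Serum ferritin uses a 12-week baseline mean (SAP 10.5.4). The inconsistency that stands is with the platelet and neutrophil rows of the same shift table.
- **That the cross-over column is distorted by a known amount.** SAP 11 lists that column, but the SAP does not state a separate baseline for cross-over subjects. Open-label laboratory data are local only (SAP 11.4), which is a separate comparability problem.

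**Conclusion.** The point holds as a minor one about descriptive safety tables. With no true change, the highest-of-two baseline lowers within-arm mean leukocyte change by about 0.56 within-subject SD if the two pre-dose readings are independent. That is about 8% to 16% at an assumed CV of 15% to 30%, and about 8% at CV 20% if the readings correlate 0.5. The direction is certain at any non-zero variability when two distinct pre-dose readings exist; the size rests on assumed CVs. The size of the leukopenia tilt also depends on the assumed median WBC and LLN.

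The effect is confined to leukocyte change from baseline and the baseline category of the leukopenia shift table, in within-arm and uncontrolled luspatercept summaries. Post-baseline grades, including counts reaching Grade 3 or higher, do not move, and no efficacy result is touched.

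**What to change.** In SAP 5.1, limit the highest-value leukocyte baseline to the >=2x and >=3x baseline threshold rows of SAP 11.4.1, including the 42-day versions and the repeats by splenectomy status. Use the SAP's standard baseline (last value on or before first dose) for leukocyte change from baseline and for the low-grade shift table. Dosing rules are not affected.

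The cost is one sentence in the SAP, plus a footnote in each affected table naming the leukocyte baseline it uses, because there will now be two. Both readings are already collected. If the sponsor keeps the present rule, the minimum is a footnote on the change and shift tables saying that the baseline is the higher of two readings and that this pulls within-arm change downwards.

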**Table 3: Table of Events (Continued)**

Assessments	Section	Screening/ Run-in Period Week -12 to Day -1	Treatment Period (double-blinded)				Long-term Treatment Period  (double- blinded) every 3-wk visits from Week 49 (ie, Dose 17 if no dose delays) /Day 1 (± 5 days)	Open-label Phase, every 3-wk visits from unblinding (± 5 days)		Day 22 Post Last Dose/ Treatment D/C 	Post-treatment Follow-up Period (± 7 days)			
			Luspatercept/ placebo Dose 1 Schedule (+7 days)		Luspatercept/placebo Doses 2 up to max 48 weeks Treatment (± 3 days)			Dose 1 for Placebo, Discont. 	Dose X Day 1 		Follow- up Week 9 (from last dose) 	Only if  Early Discont. – Follow-up Visits weeks 24, 48, 72, 96, 120, 144 (from last dose) 	All subjects: Follow- Up Visits weeks 24, 48, 72, 96, 120, 144 (from last dose) 	End of Study  / Follow- up week 156 (from last dose) 
			Day 1	Day 1	Day 8	Day 15								
Height (at Screening only)/Weight	6.1 to 6.7	X (within 4 wks prior Dose 1 Day 1)	X	X	-	-	X	X	X	X				
ECOG Performance Status	6.1 and 6.4	X (within 4 wks prior Dose 1 Day 1)	X	-	-	-	-	X	-	-	-	-	-	-
12-Lead Electrocardiogram (ECG) – read locally	6.1, 6.2, 6.4, and 6.5	X (within 4 wks prior Dose 1 Day 1)	-	-	X (Dose 6 only)	-	-	X	-	X	-	-	-	-
Cardiac Doppler Echocardiography, MUGA or MRI  ; LVEF	6.1, 6.2, 6.3	X	-	X (wk 24, wk 48 only)-	-	-	X (wk 96 only) 9	-	-	-	-	-	-	-
Pregnancy Testing 	6.1 to 6.6	X (within 4 wks prior Dose 1 Day 1; serum only)	X	X	-	-	X	X	X	X	X	-	-	-
Menstrual status (female only)	6.1 to 6.6	X	X	X	-	-	X	X	X	X	X	-	-	-

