**Table 3: Table of Events (Continued)**

Assessments	Section	Screening/ Run-in Period Week -12 to Day -1	Treatment Period (double-blinded)				Long-term Treatment Period  (double- blinded) every 3-wk visits from Week 49 (ie, Dose 17 if no dose delays) /Day 1 (± 5 days)	Open-label Phase, every 3-wk visits from unblinding (± 5 days)		Day 22 Post Last Dose/ Treatment D/C 	Post-treatment Follow-up Period (± 7 days)			
			Luspatercept/ placebo Dose 1 Schedule (+7 days)	Luspatercept/placebo Doses 2 up to max 48 weeks Treatment (± 3 days)				Dose 1 for Placebo, Discont. 	Dose X Day 1 		Follow- up Week 9 (from last dose) 	Only if  Early Discont. – Follow-up Visits weeks 24, 48, 72, 96, 120, 144 (from last dose) 	All subjects: Follow- Up Visits weeks 24, 48, 72, 96, 120, 144 (from last dose) 	End of Study  / Follow- up week 156 (from last dose) 
				Day 1	Day 1	Day 8								
Hematology  (central lab; use local lab for predose hemoglobin, in case of AE, or between doses; reticulocytes and erythroblast to be measured by local lab; in Open-label Phase – use local labs)	6.1 to 6.6	X (within 4 wks prior Dose 1 Day 1)	X	X	X (Dose 6 only)	X (Dose 6 only)	X 	X	X	X	X	-	-	-
Serum Chemistry  (predose: central lab; use local lab in case of AE, or between doses; in Open-label Phase – use local labs)	6.1 to 6.6	X (within 4 wks prior Dose 1 Day 1)	X	X	-	-	X  (every 4 doses)	X	-	X	X	-	-	-
Urinalysis: microalbumin, creatinine, microalbumin/creatinine ratio (morning void; central lab; in Open-label Phase – use local labs)	6.1.1 to 6.6	X (within 4 wks prior Dose 1 Day 1)	-	X (every 4 doses)	-	-	X  (every 4 doses)	X	-	X	X	-	-	-

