11.4 Clinical Laboratory Evaluations

Clinical laboratory data is collected by central lab and local lab (if relevant to dose administration, modification and AE, or when no central lab results are obtained). Central laboratory assessments include hematology, chemistry, immunology, and pregnancy test. Local laboratory assessments include hematology, chemistry and urinalysis. Lab data will be collected over time during the study. All summaries will be based on the SI units and missing values will not be imputed. Clinical laboratory values will be graded (grade 0-4) according to NCI-CTCAE version 4.0 for applicable tests. Normal ranges will be used to determine the “High”, “Low”, and “Normal” categories for all numeric laboratory tests. Only central lab results and local lab “Reticulocyte (Blood)” parameter will be used for table summaries.

All clinical laboratory data during the Open-label Phase were collected by local lab only. Thus, the analyses of any clinical laboratory data for the Open-label Phase will be based on local lab data.

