11.6 Electrocardiograms

The 12-lead electrocardiogram (ECG) is collected over time at selected visits. ECG parameters include heart rate, PR interval, QRS duration, RR interval and QT. The RR interval value will be derived per formula: RR interval (msec)=60000 (msec)/heart rate (bpm).

The corrected value for QT interval will be derived based on Fridericia's formula as below:

$$\text{Fridericia's formula: } QTcF = QT / (RR)^{1/3}$$

where RR is the calculated RR interval as above.

The calculated RR interval value, recorded values of other ECG parameters and change from baseline values will be summarized by visit by treatment group.

To further estimate the incidence of subjects whose baseline or post-baseline QTcF values have passed the selected ICH E14 Criteria, summary tables representing the number and percentage of subjects with ECG assessments satisfying the CPMP (Committee for Proprietary Medicinal Products) criteria will be provided for QTcF by treatment group and visit (for baseline and post-baseline respectively). A subject with baseline or any post-baseline (including 'unscheduled' visits) result meeting individual criteria will be counted. The selected CPMP criteria includes below:

Baseline/Post-baseline QTcF Interval	> 450 msec
	> 480 msec
	> 500 msec
QTcF Interval Increase from Baseline	\geq 30 msec
Post-baseline QTcF Interval and Increase from Baseline	Post-baseline Interval > 480 msec and Increase from Baseline \geq 60 msec

Corresponding listing will be provided for ECG data.

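### SAP 5.1 assigns unscheduled safety assessments to the nearest scheduled visit with no distance limit and no boundary at first dose, cross-over, unblinding or last dose

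*SAP*

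**What the plan says.** **SAP 5.1 (Reporting Conventions).** For assessments made outside the schedule, the rule reads "visits will be grouped with the closest scheduled visit based on assessment date. The average will be used as value for that scheduled visit". Averaging is for the change-from-baseline tables; shift tables take the worst category. Ties are settled: "If an unscheduled visit has equal distance to two scheduled visits, it will be grouped with the later visit". Two exceptions are made. The rule applies "except for MRI and DXA parameters", and an unscheduled ADA titer is used only where the scheduled visit has none. Baseline is defined separately, as the last value on or before first dose. Section 5.1 leaves further data selection to the individual sections, and none of SAP 11.4 to 11.7 limits the grouping by distance or by study period.

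**SAP 11 (Safety Analysis).** Unless stated otherwise, safety summaries use all collected records, including those after the primary database lock. Four treatment groups are named, one of them for placebo subjects after cross-over, but no date cut is given for the Placebo group. For ECG (SAP 11.6), "recorded values of other ECG parameters and change from baseline values will be summarized by visit by treatment group". SAP 11.5 (vital signs) and 11.7 (LVEF) plan similar by-visit summaries.

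**Protocol Table 3.**
- Vital signs and hematology fall on Day 1 of every 3-weekly dose.
- The row "12-Lead Electrocardiogram (ECG) – read locally" has entries at screening (within 4 weeks before Dose 1), Dose 6 Day 8, the open-label Dose 1 column and Day 22 post last dose. It has none at open-label Dose X Day 1.
- LVEF is scheduled at screening, Weeks 24 and 48, and Week 96 in the Long-term Treatment Period. It has no open-label or discontinuation entry.
- Footnote 18 ties the open-label Dose 1 column to placebo subjects who had discontinued. Footnote 19 has subjects still on treatment carry on with their dose numbering. Protocol 6.4 likewise asks for the extra open-label ECG only from placebo subjects in post-treatment follow-up at unblinding.

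**The concern.** Nearest-visit grouping does little harm when visits are close together and nothing changes between them. Here some measures are scheduled months apart, and the nearest visit can lie on the other side of the first dose, the switch from placebo to luspatercept, or unblinding. The rule then puts an on-treatment result into a pre-dose visit, or averages a result from one study period into another.

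Unscheduled tests are often prompted by a clinical problem, so the values misplaced in time may be the ones a safety reader most wants to see in place. The final CSR adds years of open-label follow-up, which makes the missing limits matter more.

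**Working it through.** The plan gives no figure of its own here, so the check applies the rule to the schedule.

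**Inputs.** Dosing is every 21 days (Protocol 6.2), so Dose 2 Day 1 is Day 22 and Dose 6 Day 8 is 1 + 5×21 + 7 = Day 113. Screening ECG is Day −28 to Day −1 (Protocol 6.1). Screening LVEF is Day −84 to Day −1 (Table 3, screening from Week −12). Week 24 is taken as Day 169 and Week 48 as Day 337, matching the ends of the SAP 5.1 intervals.

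**Formula.** There is no Day 0, so the offset of day d is d − 1 for d ≥ 1, and d itself for negative days. The midpoint is (earlier offset + later offset)/2. A result joins the earlier visit if its offset is below the midpoint; ties go to the later visit.

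**Crossing the first dose**

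| Measure | Earlier offset | Later offset | Midpoint | Last day joined to earlier visit |
|---|---|---|---|---|
| Vital signs, reticulocytes, central laboratory samples | 0 (Day 1) | 21 (Day 22) | 10.5 | Day 11 |
| ECG, screening on Day −28 | −28 | 112 (Day 113) | 42 | Day 42 |
| ECG, screening on Day −1 | −1 | 112 | 55.5 | Day 56 |
| Echo/MUGA LVEF, screening on Day −84 | −84 | 168 (Day 169) | 42 | Day 42 |
| Echo/MUGA LVEF, screening on Day −1 | −1 | 168 | 83.5 | Day 84 |

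For 3-weekly measures, Days 2–11 are 10 of the 20 days between the first two doses (Days 2–21).

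**Crossing unblinding, ECG.** A subject on treatment at unblinding has scheduled ECGs at Day 113 and then only at the Day 22 post-last-dose visit. The documents do not fix that day, so two values are assumed:
- Visit on Day 1009: midpoint (112 + 1008)/2 = 560, so ECGs up to Day 560 join the blinded Dose 6 Day 8 visit.
- Visit on Day 1827 (about 5 years): midpoint (112 + 1826)/2 = 969, so ECGs up to Day 969 do.

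**Crossing treatment, ECG.** On footnotes 18–19 and Protocol 6.4, a placebo subject still on treatment at unblinding follows the Dose X Day 1 column, which has no ECG. The same arithmetic then lets an unscheduled ECG taken on luspatercept be averaged into that subject's placebo-period Day 113 value.

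**Crossing unblinding, LVEF.** After Week 48 (or Week 96, if reached in the Long-term Treatment Period) no later LVEF visit exists. Any later unscheduled echocardiogram or MUGA scan maps back, however late. For example, one on Day 1009 would join Week 48 although it lies 1009 − 337 = 672 days (96 weeks) after it.

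**Crossing unblinding, vital signs.** With 21 days between visits, only results up to 10 days after the last blinded visit map back. If the next visit is 5 days late (26 days apart, tie at 13 to the later visit), this becomes 12 days.

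**The case against.** A reader might infer much more: that local open-label chemistry is averaged with central blinded-period chemistry, and that open-label abnormalities appear as worst-grade shifts at blinded visits. The documents do not support this. SAP 11.4 limits table summaries to central results plus local reticulocytes, and adds that "the analyses of any clinical laboratory data for the Open-label Phase will be based on local lab data". SAP 11.4.1 specifies central panels for the by-visit change tables. It also says "A shift table representing the shift from the baseline grade to maximum NCI-CTC Grades (high or low) will be provided" for selected parameters; it does not restate the source there, but the SAP 11.4 limit covers table summaries generally.

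Other limits also stand:
- Chemistry taken because of an adverse event or between doses is normally local: Table 3 says "use local lab in case of AE, or between doses; in Open-label Phase – use local labs". Hematology has a similar instruction. The Days 2–11 effect therefore reaches reticulocytes and central unscheduled samples, not most event-driven laboratory tests.
- No shift tables are planned for vital signs, ECG or LVEF, and LVEF measured by MRI is exempt from the rule.
- Post-dose values cannot enter the baseline used for change, because baseline has its own definition.
- Cross-over luspatercept has its own safety group, and in subjects continuing luspatercept the drug does not change at unblinding.
- The SAP does not say whether a screening or Dose 1 Day 1 row will be shown, and no frequency of unscheduled tests is given.

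These points narrow the concern without removing it. If the pre-dose row is shown, it contains on-treatment values; if not, those values drop out of the by-visit tables. Naming a cross-over group does not say that records are split at cross-over before visits are assigned. SAP 10 states such a cut for efficacy, but SAP 11 states none for safety.

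**Conclusion.** The point holds in limited form and should be corrected. Followed literally, SAP 5.1 moves early on-treatment values into pre-dose visits: Days 2–11 for 3-weekly measures, up to Day 42–56 for ECG, and up to about Day 42–84 for echocardiography or MUGA LVEF. It also lets ECG and non-MRI LVEF values cross unblinding and, for placebo subjects who cross over while on treatment, cross from luspatercept into a placebo-period visit.

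The damage is confined to descriptive by-visit safety summaries. Baseline values, transfusion endpoints (which use fixed day intervals), MRI and DXA parameters, any-post-baseline threshold tables, adverse-event tables and listings are unaffected.

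The day limits assume visits on their nominal dates. The Day 560 and Day 969 figures rest on assumed discontinuation visits. The cross-over case rests on reading footnotes 18–19 with Protocol 6.4 as giving no open-label ECG to placebo subjects still on treatment. How many results would be misplaced cannot be estimated from the documents.

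**What to change.** In SAP 5.1, before any visit is assigned:

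1. Place each unscheduled assessment in its study period: before or after first dose; before or after first luspatercept dose for cross-over subjects; before or after unblinding; before or after last dose.
2. Never group a post-dose value with a pre-dose visit, or any value with a visit in another period.
3. Within a period, group with the closest scheduled visit only inside a stated maximum window, set to suit each measure's schedule.
4. Keep values outside the window in the any-post-baseline summaries and listings.

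This costs SAP wording and visit-assignment code, with no new data. The downside is that a few unscheduled values no longer appear in a by-visit row. Using the scheduled value where one exists, instead of averaging, would follow the SAP's own handling of ADA titers, but it is optional and not needed to cure this problem.
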